11.5 Appendix 5. Contraceptive Guidance and Collection of Pregnancy and Lactation Information

Study-specific contraception requirements for male and female subjects of childbearing potential are outlined in Section 5.2. Contraceptive use and methods should be consistent with local regulations for subjects participating in clinical studies.

Male and female subjects of childbearing potential must receive pregnancy prevention counseling and be advised of the risk to the fetus if they become pregnant or father a child during treatment and for an additional 7 days after the last dose of AMG 510.

Additional medications given during the study may alter the contraceptive requirements. These additional medications may require female subjects to use highly effective methods of contraception and/or for an increased length of time. In addition, male subjects may also be required to use contraception. The investigator must discuss these contraceptive changes with the subject.

Definition of Females of Childbearing Potential

A female is considered fertile following menarche and until becoming post-menopausal unless permanently sterile. Permanent sterilization methods include documented hysterectomy, bilateral salpingectomy, and bilateral oophorectomy. Females with documented permanent infertility due to an alternate medical cause (eg, Mullerian agenesis, androgen insensitivity, gonadal dysgenesis), can be considered not of childbearing potential.

Note: Bilateral tubal ligation/occlusion is not considered a permanent sterilization method.

Note: Documentation from the following sources is acceptable to provide confirmation of each sterilization method: 1) review of subject's medical records; 2) subject's medical examination; or 3) subject's medical history interview.

A postmenopausal female is defined as:

- A woman of ≥ 55 years with no menses for 12 months without an alternative medical cause OR
- A woman age < 55 years with no menses for at least 12 months and with a folliclestimulating hormone (FSH) level within the definition of "postmenopausal range" for the laboratory involved. In the absence of 12 months of amenorrhea, confirmation with more than one FSH measurement is required.

Contraception Methods for Female Subjects

Highly Effective Contraceptive Methods

Note: Failure rate of < 1% per year when used consistently and correctly.

- Intrauterine device
- Bilateral tubal ligation/occlusion
- Vasectomized partner (provided that partner is the sole sexual partner of the female subject of childbearing potential and that the vasectomized partner has received medical assessment of the surgical success)
- Sexual abstinence (defined as refraining from heterosexual intercourse during the entire period of risk associated with the study treatments; the reliability of sexual abstinence must be evaluated in relation to the duration of the trial and the preferred and usual lifestyle of the subject)

Contraception Methods for Male Subjects

- Sexual abstinence (defined as refraining from heterosexual intercourse during the entire period of risk associated with protocol-required therapies; the reliability of sexual abstinence must be evaluated in relation to the duration of the trial and the preferred and usual lifestyle of the subject)
- Use a condom during treatment and for an additional 7 days after the last dose of protocol-required therapies

The female partner should consider using an acceptable method of effective contraception such as: hormonal, intrauterine device, intrauterine hormonal-releasing system, female barrier method (diaphragm, cap, sponge [a female condom is not an option because there is a risk of tearing when both partners use a condom]).

Note: If the male's sole female partner is of non-childbearing potential or has had a bilateral tubal ligation/occlusion, he is not required to use additional forms of contraception during the study.

Unacceptable Methods of Birth Control for Male and Female Subjects

Birth control methods that are considered unacceptable in clinical trials include:

- periodic abstinence (calendar, symptothermal, post-ovulation methods)
- withdrawal (coitus interruptus)
- spermicides only
- lactational amenorrhea method

Collection of Pregnancy Information

Female Subjects Who Become Pregnant

• Investigator will collect pregnancy information on any female subject who becomes pregnant while taking protocol-required therapies through an additional 7 days after the last dose of AMG 510.

- Information will be recorded on the Pregnancy Notification Form (see Figure 11-2). The form must be submitted to Amgen Global Patient Safety within 24 hours of the site's awareness of a subject's pregnancy. (Note: Sites are not required to provide any information on the Pregnancy Notification Form that violates the country or regions local privacy laws).
- After obtaining the female subject's signed authorization for release of pregnancy and infant health information, the investigator will collect pregnancy and infant health information and complete the pregnancy questionnaire for any female subject who becomes pregnant while taking protocol-required therapies through the end of study visit. This information will be forwarded to Amgen Global Patient Safety. Generally, infant follow-up will be conducted up to 12 months after the birth of the child (if applicable).
- Any termination of pregnancy will be reported to Amgen Global Patient Safety, regardless of fetal status (presence or absence of anomalies) or indication for procedure.
- While pregnancy itself is not considered to be an adverse event or serious adverse event, any pregnancy complication or elective termination of a pregnancy for medical reasons will be reported as an adverse event or serious adverse event. Abnormal pregnancy outcomes (eg, spontaneous abortions, stillbirth, fetal death, congenital anomalies) will be reported as an adverse event or serious adverse event. Note that an elective termination with no information on a fetal congenital malformation or maternal complication is generally not considered an adverse event, but still must be reported to Amgen as a pregnancy exposure case.
- Any serious adverse event occurring as a result of a post-study pregnancy which is considered reasonably related to the study treatment by the investigator, will be reported to Amgen Global Patient Safety as described in Section 11.4. While the investigator is not obligated to actively seek this information in former study subjects, he or she may learn of a serious adverse event through spontaneous reporting.
- Any female subject who becomes pregnant while participating will discontinue study treatment (see Section 7.1 for details).

Male Subjects With Partners Who Become Pregnant

- In the event a male subject fathers a child during treatment, and for an additional 7 days after discontinuing protocol-required therapies, the information will be recorded on the Pregnancy Notification Form. The form (see Figure 11-2) must be submitted to Amgen Global Patient Safety within 24 hours of the site's awareness of the pregnancy. (Note: Sites are not required to provide any information on the Pregnancy Notification Form that violates the country or regions local privacy laws).
- The investigator will attempt to obtain a signed consent for release of pregnancy and infant health information directly from the pregnant female partner to obtain additional pregnancy information.
- After obtaining the female partner's signed consent for release of pregnancy and infant health information, the investigator will collect pregnancy outcome and infant health information on the pregnant partner and her baby and complete the pregnancy questionnaires. This information will be forwarded to Amgen Global Patient Safety.

- Generally, infant follow-up will be conducted up to 12 months after the birth of the child (if applicable).
- Any termination of the pregnancy will be reported to Amgen Global Patient Safety regardless of fetal status (presence or absence of anomalies) or indication for procedure.

Collection of Lactation Information

- Investigator will collect lactation information on any female subject who breastfeeds while taking protocol-required therapies through an additional 7 days after the last dose of AMG 510.
- Information will be recorded on the Lactation Notification Form (see Figure 11-2 below) and submitted to Amgen Global Patient Safety within 24 hours of the investigator's awareness of the event.
- Study treatment will be discontinued if female subject breastfeeds during the study as described in exclusion criterion 215.
- With the female subjects signed consent for release of mother and infant health information, the investigator will collect mother and infant health information and complete the lactation questionnaire on any female subject who breastfeeds while taking protocol-required therapies through the end of study visit after discontinuing protocol-required therapies.

Figure 11-2. Pregnancy and Lactation Notification Forms

Amgen Proprietary - Confidential

AMGEN[®] Pregnancy Notification Form

Report to Amgen at: USTO [contact], Non-US [contact] or email (worldwide): [contact]

Contact Information					
/estigator Name				Site #	
none ()	Fax ()		Email	
stitution					
ddress					
0					
Subject Information	Subject Con	deru 🗆 Fomolo		ubicat and (at anost) (in)	(0010)
JDject ID #	Subject Gen	der: 📋 Female		ubject age (at onset):(in)	(ears)
Amgen Product Expos	sure				
Amgen Product	Dose at time of	Frequency	Route	Start Date	
AMG 510	conception	. ,			
AIMG 510				mm/dd/yyy	у
Was the Amgen product (or If yes, provide product (Did the subject withdraw fror	or study drug) stop da	te: mm/dd		_	
If yes, provide product (Did the subject withdraw fror . Pregnancy Information	or study drug) stop da n the study? Yes	te: mm/dd □ ^{No}	/уууу		
If yes, provide product (Did the subject withdraw fror . Pregnancy Information regnant female's last menstrual	or study drug) stop da n the study? Yes n n period (LMP) mi	te: mm/dd □ ^{No} m/ dd	/уууу		□ N/A
If yes, provide product (Did the subject withdraw fror . Pregnancy Information regnant female's last menstrual	or study drug) stop da m the study? Yes period (LMP) Mi	te: mm/dd □ No m/ dd yyyy	/yyyy	Unknown	□ N/A
If yes, provide product (Did the subject withdraw from Pregnancy Information regnant female's last menstrual Estimated date of delivery mm_ If N/A, date of termination (a	or study drug) stop da m the study? Yes n period (LMP)/ / dd/ ctual or planned) mm/	te: mm/dd No m/ dd yyyy/ dd/ yyy	/yyyy / yyyy y	Unknown	□ N/A
If yes, provide product (Did the subject withdraw from Pregnancy Information regnant female's last menstrual Estimated date of delivery mm_	or study drug) stop da n the study?Yes 1 period (LMP) mi / dd/ ctual or planned) mm delivered?Yes	te: mm/dd No m/ dd yyyy/ dd/ yyy / dd/ yyy	/yyyy / yyyyy y wm N/A	Unknown	□ N/A

Form Completed by: Print Name:	Title:
Signature:	Date:

FORM-115199

Version 1.0

Effective Date: 24-Sept-2018

[figure not shown]
AMGEN

AMGEN[®] Lactation Notification Form

Report to Amgen at: USTO [contact], Non-US [contact] or email (worldwide): [contact]

1. Case Administrative Inf	formation					
Protocol/Study Number: 201901	47					
Study Design: 🗹 Interventional 🗌 Observational (If Observational: 🗌 Prospective 🗌 Retrospective)						
2. Contact Information				0.44		
Investigator Name				Site #		
Phone ()	Fax (_)		Email		
Institution						
Address						
3. Subject Information						
Subject ID #	Subject age (a	at onset): (in ye	ars)			
4. Amgen Product Exposu	ure					
	Dose at time of		_			
Amgen Product	breast feeding	Frequency	Route	Start Date		
AMG 510				mm/dd/yyyy		
						
Was the Amgen product (or st	tudv drug) discontinue	ed? 🗌 Yes 🗌 N	lo			
If yes, provide product (or						
Did the subject withdraw from				_		
	, .					
5. Breast Feeding Informa	ation					
Did the mother breastfeed or provi	ide the infant with pun	nped breast milk wh	le activelv tak	king an Amgen product? □Yes □No		
If No, provide stop date: m			,			
Infant date of birth: mm/d						
Infant gender: Female						
Is the infant healthy? Yes	No Unknown	□ N/A				
If any Adverse Event was experier	nced by the mother or	the infant, provide t	orief details:			
Form Completed by:						
Print Name:						
		TIT	e:			
		Tit	e:			
Signature:						

11.6 Appendix 6. Sample Storage and Destruction

Any blood or tissue samples collected according to the Schedule of Activities (Table 1-1) can be analyzed for any of the tests outlined in the protocol and for any tests necessary to minimize risks to study subjects. This includes testing to ensure analytical methods produce reliable and valid data throughout the course of the study. This can also include, but is not limited to, investigation of unexpected results, incurred sample reanalysis, and analyses for method transfer and comparability.

All samples and associated results will be coded prior to being shipped from the site for analysis or storage. Samples will be tracked using a unique identifier that is assigned to the samples for the study. Results are stored in a secure database to ensure confidentiality.

If informed consent is provided by the subject, Amgen can perform additional testing on remaining samples (ie, residual and back-up) to investigate and better understand the solid tumors, the dose response and/or prediction of response to AMG 510, and characterize aspects of the molecule (eg, mechanism of action/target, metabolites). Results from this analysis are to be documented and maintained but are not necessarily reported as part of this study. Samples can be retained for up to 20 years.

Since the evaluations are not expected to benefit the subject directly or to alter the treatment course, the results of pharmacogenetic or other exploratory studies are not placed in the subject's medical record and are not to be made available to the subject, members of the family, the personal physician, or other third parties, except as specified in the informed consent.

The subject retains the right to request that the sample material be destroyed by contacting the investigator. Following the request from the subject, the investigator is to provide the sponsor with the required study and subject number so that any remaining samples and any other components from the cells can be located and destroyed. Samples will be destroyed once all protocol-defined procedures are completed. However, information collected from samples prior to the request for destruction, will be retained by Amgen.

The sponsor is the exclusive owner of any data, discoveries, or derivative materials from the sample materials and is responsible for the destruction of the sample(s) at the request of the subject through the investigator, at the end of the storage period, or as appropriate (eg, the scientific rationale for experimentation with a certain sample type no

longer justifies keeping the sample). If a commercial product is developed from this research project, the sponsor owns the commercial product. The subject has no commercial rights to such product and has no commercial rights to the data, information, discoveries, or derivative materials gained or produced from the sample. See Section 11.3 for subject confidentiality.

Subjects with abnormal hepatic laboratory values (ie, alkaline phosphatase [ALP], aspartate aminotransferase [AST], alanine aminotransferase [ALT], total bilirubin [TBL]) and/or international normalized ratio (INR) and/or signs/symptoms of hepatitis (as described below) may meet the criteria for withholding or permanent discontinuation of Amgen investigational product or other protocol-required therapies, as specified in the *Guidance for Industry Drug-Induced Liver Injury: Premarketing Clinical Evaluation, July 2009*.

Criteria for Withholding and/or Permanent Discontinuation of Amgen Investigational Product and Other Protocol-required Therapies Due to Potential Hepatotoxicity

The following stopping and/or withholding rules apply to subjects for whom another cause of their changes in liver biomarkers (TBL, INR and transaminases) has not been identified.

Important alternative causes for elevated AST/ALT and/or TBL values include, but are not limited to:

- hepatobiliary tract disease
- viral hepatitis (eg, hepatitis A/B/C/D/E, Epstein-Barr Virus, cytomegalovirus, herpes simplex virus, varicella, toxoplasmosis, and parvovirus)
- right sided heart failure, hypotension or any cause of hypoxia to the liver causing ischemia
- exposure to hepatotoxic agents/drugs or hepatotoxins, including herbal and dietary supplements, plants and mushrooms
- heritable disorders causing impaired glucuronidation (eg, Gilbert's syndrome, Crigler-Najjar syndrome) and drugs that inhibit bilirubin glucuronidation (eg, indinavir, atazanavir)
- alpha-one antitrypsin deficiency
- alcoholic hepatitis
- autoimmune hepatitis
- Wilson's disease and hemochromatosis
- nonalcoholic fatty liver disease including steatohepatitis
- non-hepatic causes (eg, rhabdomyolysis, hemolysis)

If investigational product(s) is/are withheld, the subject is to be followed for possible drug induced liver injury (DILI) according to recommendations in the last section of this appendix.

Page 99 of 109

Rechallenge may be considered if an alternative cause for impaired liver tests (ALT, AST, ALP) and/or elevated TBL, is discovered and/or the laboratory abnormalities resolve to normal or baseline (see next section in this appendix).

Table 11-2. Conditions for Withholding and/or Permanent Discontinuation ofAmgen Investigational Product and Other Protocol-required Therapies Due toPotential Hepatotoxicity

Analyte	Temporary Withholding	Permanent Discontinuation
TBL	> 3 x ULN at any time	> 2 x ULN
		OR
INR		> 1.5 x (for subjects not on anticoagulation therapy)
	OR	AND
AST/ALT	 > 5 x ULN at any time > 3 x ULN with clinical signs or symptoms that are consistent with hepatitis (such as right upper quadrant pain/tenderness, fever, nausea, vomiting, and jaundice) OR 	In the presence of no important alternative causes for elevated AST/ALT and/or TBL values > 3 x ULN (when baseline was < ULN)
ALP	> 8 x ULN at any time	

ALP = alkaline phosphatase; ALT = alanine aminotransferase; AST = aspartate aminotransferase; INR = international normalized ratio; TBL = total bilirubin; ULN = upper limit of normal

Criteria for Rechallenge of Amgen Investigational Product and Other Protocol-required Therapies After Potential Hepatotoxicity

The decision to rechallenge the subject is to be discussed and agreed upon unanimously by the subject, investigator, and Amgen.

Subjects who clearly meet the criteria for permanent discontinuation (as described in Table 11-2) are never to be rechallenged.

Drug-induced Liver Injury Reporting and Additional Assessments

Reporting

To facilitate appropriate monitoring for signals of DILI, cases of concurrent AST or ALT and TBL and/or INR elevation, according to the criteria specified in the above, require the following:

- The event is to be reported to Amgen as a serious adverse event within 24 hours of discovery or notification of the event (ie, before additional etiologic investigations have been concluded)
- The appropriate CRF (eg, Event CRF) that captures information necessary to facilitate the evaluation of treatment-emergent liver abnormalities is to be completed and sent to Amgen

Other events of hepatotoxicity and potential DILI are to be reported as serious adverse events if they meet the criteria for a serious adverse event defined in Section 11.4.

Additional Clinical Assessments and Observation

All subjects in whom investigational product(s) or protocol-required therapies is/are withheld (either permanently or conditionally) due to potential DILI as specified in Table 11-2 or who experience AST or ALT elevations > 3 x upper limit of normal (ULN) or 2-fold increases above baseline values for subjects with elevated values before drug are to undergo a period of "close observation" until abnormalities return to normal or to the subject's baseline levels.

Assessments that are to be performed during this period include:

- Repeat AST, ALT, ALP, bilirubin (BIL) (total and direct), and INR within 24 hours
- In cases of TBL > 2x ULN or INR > 1.5, retesting of liver tests, BIL (total and direct), and INR is to be performed every 24 hours until laboratory abnormalities improve

Testing frequency of the above laboratory tests may decrease if the abnormalities stabilize or the investigational product(s) or protocol-required therapies has/have been discontinued AND the subject is asymptomatic.

Initiate investigation of alternative causes for elevated AST or ALT and/or elevated TBL. The following are to be considered depending on the clinical situation:

- complete blood count with differential to assess for eosinophilia
- serum total immunoglobulin (Ig)G, anti-nuclear antibody anti-smooth muscle antibody, and liver kidney microsomal antibody-1 to assess for autoimmune hepatitis
- serum acetaminophen (paracetamol) levels

- a more detailed history of:
 - prior and/or concurrent diseases or illness
 - exposure to environmental and/or industrial chemical agents
 - symptoms (if applicable) including right upper quadrant pain, hypersensitivity-type reactions, fatigue, nausea, vomiting and fever
 - prior and/or concurrent use of alcohol, recreational drugs and special diets
 - concomitant use of medications (including non-prescription medicines and herbal and dietary supplements), plants, and mushrooms
- Viral serologies
- creatine phosphokinase, haptoglobin, lactate dehydrogenase and peripheral blood smear
- appropriate liver imaging if clinically indicated
- appropriate blood sampling for pharmacokinetic analysis if this has not already been collected
- hepatology consult (liver biopsy may be considered in consultation with a hepatologist)

Follow the subject and the laboratory tests (ALT, AST, TBL, INR) until all laboratory abnormalities return to baseline or normal or considered stable by the investigator. The "close observation period" is to continue for a minimum of 4 weeks after discontinuation of all investigational product(s) and protocol-required therapies.

The potential DILI event and additional information such as medical history, concomitant medications and laboratory results must be captured in the corresponding CRFs.

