- 110 Adequate hematological laboratory assessments, as follows:
 - absolute neutrophil count (ANC) \geq 1.5 x 10⁹/L
 - platelet count \ge 75 x 10⁹/L
 - hemoglobin \ge 9 g/dL (90 g/L)
- 111 Adequate renal assessments, as follows:
 - estimated glomerular filtration rate based on Modification of Diet in Renal Disease (MDRD) calculation ≥ 60 mL/min/1.73 m²
- 112 Adequate hepatic laboratory assessments, as follows:
 - aspartate aminotransferase (AST) < 2.5 x upper limit of normal (ULN) (if liver metastases are present, ≤ 5 x ULN)
 - alanine aminotransferase (ALT) < 2.5 x ULN (if liver metastases are present, \leq 5 x ULN)
 - total bilirubin (TBL) < 1.5 x ULN (< 2.0 x ULN for subjects with documented Gilbert's syndrome or < 3.0 x ULN for subjects for whom the indirect bilirubin level suggests an extrahepatic source of elevation)
- 113 Adequate coagulation laboratory assessments, as follows
 - prothrombin time (PT) or partial thromboplastin time (PTT) < 1.5 x ULN, or international normalized ratio (INR) < 1.5 or within target range if on prophylactic anticoagulation therapy

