6.2.4 Hepatotoxicity Stopping and Rechallenge Rules

Refer to Section 11.7 for details regarding drug-induced liver injury guidelines, as specified in the *Guidance for Industry Drug-Induced Liver Injury: Premarketing Clinical Evaluation, July* 2009.

Guidelines for management and monitoring of subjects with increased AST, ALT, or alkaline phosphatase are outlined in Table 6-4.

	Table 6-4. AMG 5	10 Hepatotoxicity Gui	delines		
 If the conditions for permanent discontinuation are met (below): Subject to be permanently discontinued AST or ALT > 3 x ULN and INR > 1.5 x ULN (for subjects not on anticoagulation therapy) in the presence of no important alternative causes for elevated AST/ALT values OR					
CTCAE Grade	AMG 510 Action	Medical Management	Monitoring and Follow-up		
Grade 2 AST or ALT and ALP ≤ 8 x ULN with no clinical symptoms consistent with hepatitis (right upper quadrant pain/tenderness, fever, nausea, vomiting, and jaundice)	Continue	Consider steroids ^b	Closely monitor liver function tests		
	First Occurrence		Closely monitor liver function tests		
Grade 2 AST or ALT	Withhold	Initiate steroids ^b	 Await resolution to baseline or grade 1 and resolution or improvement of hepatitis symptoms Restart at 1 dose level reduction^{c, e} 		
with symptoms Or	Second Occurrence		Closely monitor liver function tests		
Grade 3 or 4 AST or ALT Or	Withhold	Initiate steroids ^b	 Await resolution to baseline or grade 1 and resolution or improvement of hepatitis symptoms Resume at an additional 1 dose level reduction only with MEDICAL MONITOR approval^{c, e} 		
8x ULN ALP ^d	Third Occurrence				
	Permanently		NOT APPLICABLE		

Table 6-4. AMG 510 Hepatotoxicity Guidelines

ALP = alkaline phosphatase; ALT = alanine aminotransferase; AST = aspartate aminotransferase; CTCAE = Common Terminology Criteria for Adverse Events; INR = international normalized ratio; LFT = liver function test; TBL = total bilirubin; ULN = upper limit of normal

^a If increase in AST/ALT is likely related to alternative agent, discontinue causative agent and await resolution to baseline or grade 1 prior to resuming AMG 510.

^b For example: prednisone 1.0 to 2.0 mg/kg/day, dexamethasone equivalent, or methylprednisolone equivalent, followed by a taper. The taper may occur after restarting AMG 510.

^c Close monitoring at restart (eg, daily LFTs x 2, then weekly x 4). AMG 510 dose may be increased after discussion with medical monitor.

discontinue AMG 510

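### Table 6-4 and Appendix 7 both govern liver toxicity but differ on permanent discontinuation for subjects with raised baseline AST/ALT, and on the recovery and agreement needed before restart

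*Protocol*

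**What the plan says.** **Which text applies.** Footnote b of Table 6-3 directs suspected hepatotoxicity to Sections 6.2.4 and 11.7 together. Section 6.2.4 itself opens by pointing to Section 11.7 and then presents Table 6-4. No order of precedence is given.

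**Permanent discontinuation.** The first condition in Table 6-4 is "AST or ALT > 3 x ULN and INR > 1.5 x ULN (for subjects not on anticoagulation therapy", provided nothing else important explains the raised AST/ALT. Table 11-2 combines bilirubin above 2 x ULN or INR "> 1.5 x (for subjects not on anticoagulation therapy" with an AST/ALT limit of "> 3 x ULN (when baseline was < ULN", again with no important alternative cause. Appendix 7 then bars rechallenge for subjects who clearly meet the Table 11-2 criteria. It does not mention those of Table 6-4.

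**Entry limits.** Inclusion criterion 112 allows "aspartate aminotransferase (AST) < 2.5 x upper limit of normal (ULN) (if liver metastases are present, ≤ 5 x ULN", and sets the same limits for ALT. Raised baseline values are therefore eligible with or without liver metastases.

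**Restart.** At a first occurrence Table 6-4 says "Restart at 1 dose level reduction" once values are back to baseline or grade 1 and symptoms have resolved or improved; no approver is named. At a second occurrence treatment resumes only "with MEDICAL MONITOR approval". In Appendix 7 the decision must be "agreed upon unanimously by the subject, investigator, and Amgen", whatever the occurrence. Rechallenge may be considered there if another cause is found and/or the abnormalities resolve to normal or baseline.

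**The concern.** Section 2.3 names increases in AST and ALT among the key clinical risks to be monitored, so these rules are likely to be used. If the two sources give different instructions for one event, whether a subject stays on drug may depend on which page the site consults.

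The first consequence is for the subject's safety. The second is for the data: whether the event counts as an adverse event leading to withdrawal, whether a dose reduction is recorded, and how much exposure accrues. With at most 18 subjects in all and 6 to 12 per cohort, those summaries are sensitive to a single case.

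**Working it through.** No figure in the plan depends on this point, so the check compares the rules as logical conditions.

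**Step 1: permanent discontinuation.** AST/ALT, baseline, bilirubin and INR are expressed as multiples of ULN. Table 11-2 does not name the multiplicand for INR; I read it as ULN, as in Table 6-4, so that INR is not itself a source of difference.

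- Table 6-4, INR condition: ALT > 3 and INR > 1.5, not anticoagulated, no important alternative cause.
- Table 11-2: (bilirubin > 2 or INR > 1.5) and ALT > 3 and baseline < 1, not anticoagulated for the INR part, no important alternative cause.

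Take INR 1.6, normal bilirubin, no anticoagulation and no alternative cause, with on-study ALT of 3.5 or 6.0:

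| Baseline ALT (x ULN) | Eligible under criterion 112 | Table 6-4 | Table 11-2 |
|---|---|---|---|
| 0.8 | yes | permanent stop | permanent stop |
| 1.0 | yes | permanent stop | no permanent stop |
| 1.5 | yes | permanent stop | no permanent stop |
| 2.4 | yes | permanent stop | no permanent stop |
| 4.0 | only with liver metastases | permanent stop | no permanent stop |

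Each row is the same at both ALT values. The rules agree below ULN and part at ULN and above. At ALT 6.0 the subjects in the last four rows meet only the temporary withholding limit of Table 11-2 (above 5 x ULN). Because the bar on rechallenge is tied to Table 11-2, Appendix 7 leaves rechallenge open to subjects whom Table 6-4 has stopped permanently.

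**Step 2: restart, side by side.**

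| | Table 6-4 | Appendix 7 |
|---|---|---|
| Agreement, first occurrence | none named | subject, investigator and Amgen, unanimous |
| Agreement, second occurrence | medical monitor | the same three-party agreement |
| Recovery level | baseline or grade 1 | normal or baseline (resolution route) |

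Consider a subject with normal baseline ALT and a first grade 3 ALT event after cycle 1, chosen so that the first-cycle dose-limiting toxicity rule does not enter. ALT falls to grade 1, symptoms are absent and no other cause is found. Table 6-4 restarts one dose level lower with no named approver. On the resolution route of Appendix 7, ALT has reached neither normal nor baseline, and three parties would have to agree.

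**Step 3: weight of one subject.** 1/6 = 16.7% and 1/12 = 8.3%. These are the shares that one differently managed subject contributes to a cohort percentage. They say nothing about how likely the event is.

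**The case against.** **The table is damaged in the available text.** The discontinuation block of Table 6-4 breaks off after an OR, and the anchor of footnote a is missing. A baseline note in the lost part cannot be wholly excluded. That caution stands. However, the INR condition is readable and carries no such limit, and an alternative joined by OR cannot narrow it. Nothing here rests on the unreadable condition.

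**The rules could be cumulative.** A site could meet Table 6-4 and also obtain the agreement required by Appendix 7, and silence at the first occurrence is not an express waiver. This is the best counter-argument, but the text does not fit it well. If the stricter rule always applied, the baseline qualifier in Table 11-2 would do nothing in INR cases, and separate medical monitor approval at the second occurrence would add nothing if Amgen must always agree. Nor can the Table 6-4 restarts be set apart as something other than rechallenge, because footnote d of that table uses the term re-challenges for them.

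**Stronger readings that the documents do not support.**

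- A reader might infer that a subject with liver metastases entering above 3 x ULN must stop permanently on an INR rise alone. Table 6-4 also requires no important alternative cause. The list of such causes in Appendix 7 is open-ended and includes hepatobiliary tract disease. Whether liver metastases count is left to judgement, so the 4.0 x ULN row is the least secure.
- A reader might infer that every subject with liver metastases and raised transaminases is affected. Several conditions must coincide, and criterion 113 generally limits coagulation values at entry. Conversely, liver metastases are not needed: the rules already differ at a baseline of 1.0 x ULN.
- A reader might infer that a primary endpoint is at stake. The named primary safety endpoints are dose-limiting toxicity, treatment-emergent and treatment-related adverse events, and changes in vital signs, ECGs and laboratory tests. Adverse events leading to withdrawal are an additional descriptive tabulation, and no hypothesis is tested.

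**Conclusion.** Wrong as written: an internal inconsistency in current protocol text, in two parts.

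1. Permanent discontinuation differs for eligible subjects with baseline AST/ALT at or above ULN who, on study, have AST/ALT above 3 x ULN with INR above 1.5 x ULN, are not anticoagulated and have no important alternative cause. All these conditions must hold together, so few if any subjects will be affected. The documents give no rate from which to estimate how many.
2. Restart differs in who must agree and in the recovery level. This is the wider conflict, since it can arise at any first hepatotoxicity restart.

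The effect is on subject safety and on the descriptive summaries of adverse events leading to withdrawal, dose modification and exposure, where one subject weighs 8.3% to 16.7% of a cohort of 12 to 6. The first part assumes that the unreadable portion of Table 6-4 carries no baseline qualifier. No view is taken on which clinical rule is right.

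**What to change.** Reconcile Table 6-4 with Table 11-2 and the rechallenge text of Appendix 7 so that the protocol has:

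- one set of conditions for permanent discontinuation, stating how subjects with baseline AST/ALT at or above ULN are handled;
- a bar on rechallenge tied to that same set;
- one recovery level before restart;
- one approval requirement, with any difference by occurrence stated outright;
- a sentence saying which section governs.

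The sponsor's clinicians must choose the content of each rule. The cost is wording in the next protocol amendment and a letter to sites. No planned analysis or sample size changes.
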